#### 8.1.1.1. Definition of Serious Adverse Events

An SAE is an AE that occurs during any phase of the study (i.e., baseline, treatment, washout, or follow-up) at any dose of the investigational product, comparator, or placebo, and fulfills one or more of the following:

- Results in death
- It is immediately life-threatening
- It requires in-patient hospitalization or prolongation of existing hospitalization
- It results in persistent or significant disability or incapacity
- Results in a congenital abnormality or birth defect
- It is an important medical event that may jeopardize the subject or may require medical intervention to prevent one of the outcomes listed above.

All SAEs that occur from the day of the biopsy procedure, during treatment, or within 24 months following the final REACT injection, whether or not they are related to study procedures or the

investigational product, must be recorded in the subject's medical record as well as the CRF provided by the Sponsor or its designee.

#### **8.1.1.2. Other Significant Adverse Events**

Significant events of particular clinical importance include SAEs and AEs leading to premature discontinuation of subjects from the study. These events will be recorded in the subjects' medical records as well as the CRF provided by the Sponsor or its designee. Narratives of these events may be prepared for inclusion in the Clinical Study Report.

The following sections describe "adverse events of special interest" concerning procedure- and product-related events. Subjects should be carefully monitored for the occurrence of these potential AEs.

#### **8.1.1.3. Procedure-Related Events**

**Post-procedure pain:** If the subject experiences pain following the biopsy or REACT injection, administration of paracetamol or paracetamol-codeine combinations is recommended. More severe pain in the loin or abdomen requires ultrasonography to exclude significant perirenal hemorrhage. If severe pain occurs, administration of opiates may be necessary. If analgesic doses higher than the maximum authorized doses are required to alleviate pain, then the Investigator must perform additional clinical evaluations to ascertain the probable cause(s) of excessive pain.

**Hemorrhage:** Following renal biopsy and REACT injection procedures, subjects undergo regular hemoglobin and blood pressure monitoring. Subjects will be confined to bed and monitored for maintenance of normal coagulation indices. If bleeding occurs and the subject is hypotensive despite bed rest, a blood transfusion may be considered. If the bleeding is still not controlled, surgery may be considered. In rare cases, renal angiography may be performed to identify the source of bleeding. Coil embolization can be performed during the same procedure.

**Other complications:** In very rare cases, other organs (such as liver, gallbladder and lungs) may be penetrated during the biopsy procedure. In these cases, appropriate treatment and follow- up may be discussed with consulting surgeons.

**Death:** Deaths resulting from renal biopsies occur in <0.01% of patients. Adherence to strict inclusion /exclusion criteria will ensure that subjects who may be predisposed to uncontrolled or excessive bleeding will not be enrolled in this trial.

#### **8.1.1.4. Product-Related Events**

No REACT product-related events are expected to occur. This assumption is based on the autologous nature of REACT (i.e., REACT is manufactured from renal cells isolated from the same kidney to which they are being returned), the lack of product-related events observed in pre- clinical animal studies, and the lack of specific REACT- related events seen during and following implant of the first 5 subjects in the Phase 1 clinical trial. However, subjects will be extensively monitored throughout the course of the study for any unexpected events.

If an event occurs which is assessed as related to the investigational product, REACT, then the event will be immediately reviewed by the Investigator and Medical Monitor.

## 8.2. Adverse Event Intensity and Relationship Assessment

### 8.2.1. Intensity Scale

Intensity will be assessed by the Investigator using the “Common Terminology Criteria for Adverse Events” (CTCAE) version 4.03, from the US National Cancer Institute (refer to [http://evs.nci.nih.gov/ftp1/CTCAE/CTCAE\\_4.03\\_2010-06-14\\_QuickReference\\_8.5x11.pdf](http://evs.nci.nih.gov/ftp1/CTCAE/CTCAE_4.03_2010-06-14_QuickReference_8.5x11.pdf)).

If the AE is not included in the CTCAE, then the Investigator will determine the intensity of the AE according to the following criteria:

- **Mild (Grade 1):** The AE is noticeable to the subject but does not interfere with routine activity.
- **Moderate (Grade 2):** The AE interferes with routine activity but responds to symptomatic therapy or rest.
- **Severe (Grade 3):** The AE significantly limits the subject’s ability to perform routine activities despite symptomatic therapy. Severe events are usually incapacitating.
- **Life-Threatening (Grade 4):** The subject is at immediate risk of death.
- **Death (Grade 5)**

If the intensity (grade) changes within a day, the maximum intensity (grade) should be recorded. If the intensity (grade) changes over a longer period of time, the changes should be recorded as separate events (having separate onset and stop dates for each grade).

It is important to distinguish between serious and severe AEs. Severity is a measure of intensity whereas seriousness is defined by the criteria under Definition of Serious Adverse Events (See [Section 8.1.1.1](#)). Therefore, an AE of severe intensity may not necessarily meet the criteria for seriousness.

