#### **9.7.2. Adverse Events**

Clinical and laboratory AEs will be coded using the Medical Dictionary for Regulatory Activities (MedDRA) version 18.1 by System Organ Class (SOC) and Preferred Term (PT). Adverse events will be graded using the CTCAE version 4.03 from the US National Cancer Institute.

A treatment-emergent AE will be defined as any AE that started after the first injection of REACT or started prior to the first injection but increased in severity or frequency after the first injection of REACT. Summaries (frequency and proportion) of treatment-emergent AE's will be presented by SOC and PT. Additional summaries will include, but are not limited to, treatment- emergent AE judged to be related to the procedure and/or investigational product, intensity, reason for subject withdrawal, SAEs, and deaths. The numbers of events (occurrence) and the number of subjects (incidence) who experienced treatment-emergent AEs will be reported by treatment group. Adverse event data will be provided in a data listing.

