4.9 Analysis Periods

The following analysis periods will be defined as:

- Pre-Injection Period: from the start day of biopsy to the first REACT injection.
- Acute First Injection Period: from the first REACT injection to 1 month following the first REACT injection. The acute first injection period is a subset of the inter-injection period defined below.
- Inter-Injection Period: from the first REACT injection to either the second REACT injection or (if no such second injection was delivered) trial withdrawal or completion.
- Acute Second Injection Period: from the second REACT injection to 1 month following the second REACT injection. The acute second injection period is a subset of the post-second-injection period defined below.
- Post-Second Injection Period: from the second REACT injection to trial withdrawal or completion. This period will not apply to participants for whom only one REACT injection was delivered.
- Post-Injection Period: from the first REACT injection to trial withdrawal or completion. This period includes both the inter-injection and post-second injection periods.

[figure not shown]
If necessary, imputed dates will be used to determine the analysis period for adverse events.

Figure 1. Analysis Period Diagram for Subjects that Received Two Injections

Abbreviations: EOS = End of Study

Figure 2. Analysis Period Diagram for Subjects that Received One Injection

Abbreviations: EOS = End of Study

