7.2.1 Treatment-Emergent Adverse Events

Treatment-emergent adverse events (TEAEs) are defined as any AE that started after the first injection of REACT or started prior to the first injection but increased in severity or frequency after the first injection of REACT. For missing onset or end dates, the rules stated in [Section 4.8](#) will be followed. The imputed dates will be used to determine if the AE is treatment emergent.

In addition to the overall treatment-emergence period defined above, the analysis periods defined in [section 4.9](#) will be used for analysis of the AEs:

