- k. the number and percentage of subjects experiencing a TEAE leading to study discontinuation during the acute first injection, inter-injection, acute second injection, post-second injection, and post-injection periods
- l. the number and percentage of subjects experiencing a TEAE leading to death during the acute first injection, inter-injection, acute second injection, post-second injection, and post-injection periods

In the overall summary of AEs table, besides tabulating the number and percentage of subjects, the total number of AE episodes will also be provided. If a subject has repeated episodes of a particular AE, all episodes will be counted in the summary table.

Additionally, each of the categories of events presented in the overall summary of AEs table will be summarized by SOC and PT in individual tables. In the remaining summary tables, the incidence of TEAEs will be calculated by dividing the number of subjects who have experienced the event by the total number of subjects in the analysis set. Thus, the incidence of TEAEs is shown in terms of the total number of subjects and not in terms of the total number of episodes. If a subject has repeated episodes of a particular TEAE, only the most severe episode, or the episode with the strongest causal relationship to biopsy, REACT product, or REACT injection procedure will be counted in the summary tables.

A subject with more than one type of TEAE in a particular SOC will be counted only once in the total number of subjects experiencing TEAEs in that particular SOC. Since a subject could have more than one type of TEAE within a particular SOC, the sum of subjects experiencing different TEAEs within the same SOC could appear greater than the total number of subjects experiencing TEAEs in that SOC. Similarly, a subject who has experienced a TEAE in more than one SOC will be counted only once in the total number of subjects experiencing AEs in those SOCs.

All AEs will be presented in tables in descending order from the SOC with the highest incidence to the SOC with the lowest incidence. Within each SOC, AEs will be sorted in descending order from the PT with the highest incidence to the PT with the lowest incidence.

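### As the rules are written, an AE that began before the first injection and only eases afterwards counts as treatment-emergent, because a lasting fall in grade opens a new AE record

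*Protocol*

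**What the plan says.** - **Recording (Protocol 8.2.1).** When a grade changes over a period longer than a day, "the changes should be recorded as separate events (having separate onset and stop dates for each grade". The text does not distinguish a rise from a fall. There is one exception: "If the intensity (grade) changes within a day, the maximum intensity (grade) should be recorded".
- **Treatment emergence (SAP 7.2.1; same definition in Protocol 8.1.1 and 9.7.2).** A TEAE is "any AE that started after the first injection of REACT or started prior to the first injection but increased in severity or frequency" once that injection has been given.
- **Periods (SAP 4.9, applied to AEs by 7.2.1 and 7.2.5).** AEs are tabulated in periods around each injection. The acute second injection period, for example, runs "from the second REACT injection to 1 month following the second REACT injection".
- **Counting (SAP 7.2.5).** For the overall AE table: "If a subject has repeated episodes of a particular AE, all episodes will be counted in the summary table". For the SOC and PT tables, where a subject has repeats of the same TEAE, "only the most severe episode, or the episode with the strongest causal relationship to biopsy, REACT product, or REACT injection procedure will be counted". Protocol 9.7.2 also asks for both kinds of count: "The numbers of events (occurrence) and the number of subjects (incidence) who experienced treatment-emergent AEs will be reported".
- **What is absent.** SAP 4.8, 4.9 and 7.2 to 7.2.5 handle partial dates, missing intensity and missing relationship. They have no rule that joins the grade-change records of one illness, or that sets aside a record opened only because the grade fell.

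**The concern.** The TEAE definition has two limbs. The second is a filter: an AE already present at the first injection counts only if it worsens. The first limb looks at onset alone and has no severity condition. Once the recording rule gives an easing AE a fresh onset date after the injection, the new record passes the first limb and the filter in the second is bypassed.

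The trial is descriptive, with no hypothesis test, so the AE tables are the main result. Three things are at stake: whether a subject appears as having a TEAE, which injection period an event is shown in, and how many episodes are reported. In each case recovery from an earlier event could be displayed as a new event after an injection.

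**Working it through.** The documents give no figure on this point, so there is nothing to reproduce. The check applies the written rules to three assumed illnesses and then recounts with each illness treated as one event.

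**Inputs from the documents:** the recording rule (Protocol 8.2.1); TEAE status by onset (SAP 7.2.1); periods (SAP 4.9); first injection = Day 1 (SAP 4.3); at most 10 treated subjects (Protocol synopsis; SAP 9).

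**Assumptions:** second injection on Day 183; one month = 30 days; the days and grades below. All are illustrative.

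**Rules as written:** records = number of different consecutive grades; a record is a TEAE if its onset is after Day 1; it falls in the acute second period if its onset is after Day 183 and no later than Day 213 (183 + 30).

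| Case | Grade (onset day) | As written | As one illness |
|---|---|---|---|
| A: began before injection 1, then eases | 3 (Day -5), 2 (Day 4), 1 (Day 11) | 3 records, 2 TEAEs | 1 AE, 0 TEAEs |
| B: began before injection 2, then eases | 3 (Day 175), 2 (Day 186), 1 (Day 193) | 3 TEAE episodes: 1 inter-injection, 2 acute second | 1 TEAE: inter-injection only |
| C: wholly after injection 1 | 1 (Day 20), 2 (Day 24), 1 (Day 30) | 3 TEAE episodes | 1 TEAE episode |

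In case A both false TEAEs fall in the acute first injection period. Under SAP 4.9 that period lies inside the inter-injection period, which lies inside the post-injection period, so they appear in all three rows. In case B the illness is a genuine TEAE, because treatment emergence is defined from the first injection only; what is wrong is its extra appearance in the acute second and post-second injection periods. In case C TEAE status and period are right, and only the episode count is inflated.

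**Weight of one subject.** If the subject has no other event in the row, the row moves by 1/n:
- n = 10: 1/10 = 10 points
- n = 8: 1/8 = 12.5 points
- n = 5: 1/5 = 20 points

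Exact binomial 95% limits for x of n are the 0.025 quantile of Beta(x, n - x + 1) and the 0.975 quantile of Beta(x + 1, n - x), with the lower limit set to 0 when x = 0. For 0/10 this gives 0 to 30.8%; for 1/10 it gives 0.3 to 44.5%.

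**Which tables are affected.** The overall AE table and the protocol's event counts take the inflated episode totals. The SOC and PT tables count a subject once per term, so cases B and C do not multiply there within a period. The subject in case A would still enter the TEAE tables without having worsened.

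**The case against.** The strongest reply is that the outcome depends on reading. SAP 7.2 defines an AE as the development of a condition or the deterioration of an existing one, and a fall in grade is neither. The worsening limb of the TEAE definition can operate only across records, since each record holds one grade, so some event-level derivation seems to be presupposed. Nor does the SAP say that each record is an episode. This is a possible reading. It does not settle the matter, because Protocol 8.2.1 expressly calls the grade-change records separate events with their own onsets, and no derivation is written down that would join them again.

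Several stronger conclusions that a reader might draw are not supported:
- **That every grade change makes a new AE.** Changes within one day give a single record at the maximum grade.
- **That biopsy events would be shown as harm from the product or the injection.** Relationship is recorded separately for biopsy, injection procedure and product (SAP 7.2.3), so among the relatedness rows an easing biopsy event reaches only the biopsy-related TEAE row (SAP 7.2.5, item f). It is already a procedure-related AE under the primary endpoint, which is not defined by period.
- **That fluctuating laboratory values would swell the counts.** Protocol 8.3 does not require a laboratory change to be reported as an AE unless it is an SAE or leads to discontinuation or withdrawal.
- **That the split by period is unusable.** Biopsy complications that the investigator thinks make injection unsafe preclude treatment (Protocol 4.2, 7.5.1), eligibility is rechecked before each injection, and all AEs are listed by subject and onset date (SAP 7.2.5), so contiguous records can be seen.

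These points limit the reach of the problem. They do not remove it.

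**Conclusion.** The point holds. Following the stated rules can produce TEAEs from AEs that only improved after the first injection, place earlier AEs in the second-injection periods, and inflate episode totals. One affected subject moves a row by 10 points with 10 treated, and by more with fewer, provided that the subject has no other event in that row. How often this would occur cannot be derived from the documents, and the days and grades in the cases are assumptions. The conclusion rests on sites applying Protocol 8.2.1 as written and on the analysis using record onset dates, as SAP 4.9 and 7.2.1 indicate. The matter should be settled in the SAP, because the AE tables are the study's principal output and the remedy is cheap.

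**What to change.** Add to SAP 7.2.1 and 7.2.5:

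1. Contiguous grade-change records of the same preferred term in a subject form one episode. Link them on the collected dates. Where dates are partial, decide by documented data review without sight of the tables, not by imputed dates alone: SAP 4.8 moves unknown stop days to month end and unknown start days to the first of the month or towards the treatment start date, so imputed records need not meet.
2. Take TEAE status from the episode's first onset. If that precedes the first injection, the episode is a TEAE only if a later grade exceeds the grade present at the first injection, or if frequency increases.
3. Assign the episode to the period of its first onset. Assign it to a later period as well only if the grade rises there above the grade present when that period began.
4. Report the maximum grade reached within the period concerned. The maximum of the whole episode would be wrong: an AE at Grade 3 then Grade 1 before the first injection, rising to Grade 2 afterwards, is a Grade 2 TEAE, not a Grade 3 one.
5. A fall in grade alone creates neither a TEAE nor a new episode. Keep every individual record in the listings.

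Cost: SAP wording, one more derivation step, some review of partial dates, and slightly lower episode counts. No protocol change and no new data are needed.

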### 8.2.2. Relationship Assessment

An Investigator listed on Form FDA 1572 may make the determination of relationship to the study procedure or investigational product for each AE. The Investigator should judge whether there is a reasonable possibility that the AE may have been caused by the study procedure or investigational product. If no valid reason exists for suggesting a relationship, then the AE should be classified as “not related.” If there is any valid reason, even if undetermined, for suspecting a possible cause-and-effect relationship, then the AE should be considered “possibly related” or “related” to the study procedure or investigational product.

Definitions of relatedness categories are:

- **Not Related:** Exposure to the study treatment did not occur, or the occurrence of the AE is not reasonably related in time, or the AE is considered unlikely to be related to the study treatment.
- **Unlikely Related:** The study treatment and the AE were not closely related in time, and/or the AE could be explained more consistently by causes other than exposure to the study treatment product.
- **Possibly Related:** The study treatment and the AE were reasonably related in time, and the AE could be explained equally well by causes other than exposure to the study treatment product.

- **Related:** The study treatment and the AE were reasonably related in time, and the AE was more likely explained by exposure to the study product than by other causes, or the study treatment was the most likely cause of the AE.

For the purpose of safety analyses, all AEs judged by the Investigator to be “possibly related” or “related” will be considered treatment-related adverse events.

### 8.3. Recording and Reporting Adverse Events

Adverse events spontaneously reported by the subject and/or in response to an open question from study personnel, or revealed by observation, or documented via laboratory reports, imaging reports, consult notes, survey instruments and other data collection tools, will be recorded in the subject’s medical records and CRF provided by the Sponsor or its designee.

Adverse events will be reported using standard medical terminology, whenever possible. A clinically significant change in laboratory values or vital signs need not be reported as an AE unless the abnormal change constitutes an SAE and/or leads to discontinuation of treatment or withdrawal from the study.

For each AE, the Investigator will record the start date, the stop date, the intensity of each reportable event, the Investigator’s judgment of the relationship to the study procedure or investigational product, the action taken, severity (if applicable), and whether the event resulted in discontinuation of treatment or withdrawal from the study. Follow-up information on any SAE may be requested by ProKidney or its designee.

All SAEs must be promptly reported by the Investigator to ProKidney or its designee within 24 hours from the time when the Investigator first becomes aware of the event. All SAEs must be reported whether or not they are considered causally related to the study procedure or investigational product. SAE forms will be provided to each clinical site.

The information collected will include subject number, a narrative description of the event, and an assessment by the Investigator as to the intensity of the event and relatedness to the investigational product. The Investigator must complete, sign and date the SAE pages, and verify the accuracy of the information recorded against the corresponding source documents. Follow-up information on the SAE may be requested by ProKidney or its designee.

Contact information for reporting SAEs appears below:

Email: [[contact]](mailto:[contact])  
SAE [contact]  
eFax: [name]

ProKidney or its designee is responsible for notifying the relevant regulatory authorities of certain AEs. It is the Principal Investigator’s responsibility to notify the IRB /EC of all SAEs that occur at the site.

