#### 7.2.5. Funduscopic Exam of Retina

This exam should be completed at screening, month 12, and month 24/EOS to monitor for diabetic retinopathy of both eyes. Retinal photography should be collected and kept within the patient records and any worsening from baseline should be reported as an AE if not already documented in medical history.

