## 8. SAFETY ASSESSMENTS AND MANAGEMENT

### 8.1. Adverse and Serious Adverse Events

#### 8.1.1. Definition of Adverse Events

An AE is the development of an undesirable medical condition (including abnormal laboratory findings) or the deterioration of a pre-existing medical condition following or during exposure to a study treatment, whether or not considered to have a causal relationship with study procedures or the investigational product. A pre-existing condition is a clinical condition (including a condition being treated) that is diagnosed before the subject signs the Informed Consent Form and is documented as part of the subject's medical history. Pre-existing conditions that are stable or unchanged should not be considered AEs.

The Investigator is responsible for ensuring that all AEs observed by the Investigator or reported by the subject that occur from the day of the biopsy procedure through 24 months after the final injection of REACT are monitored and recorded in the subject's medical record as well as the CRF provided by the Sponsor or its designee.

Treatment-emergent adverse events (TEAEs) are defined as any AE that started after the first injection of REACT or started prior to the first injection but increased in severity or frequency after the first injection of REACT.

Unscheduled visits may be performed at any time during the study as judged necessary by the Investigator to assess and conduct follow-up on AEs. Evaluations and procedures to be performed at unscheduled visits will be at the Investigator's discretion in consultation with the Sponsor and may be based on those listed in the Schedule of Events.

The Investigator's clinical judgment is used to determine whether a subject is to be removed from treatment due to an AE.

An AE is considered unexpected if it is not consistent in nature or severity with information contained in the current version of the **Investigator's Brochure** provided by the Sponsor.

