2.2 Endpoints

2.2.1 Primary Endpoint

Procedure and/or product related AEs through 24 months post last injection.

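### Protocol 8.3 lets sites leave clinically significant, non-serious laboratory and vital-sign changes out of the AE record, so a related change can be missing from the primary endpoint

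*Protocol*

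**What the plan says.** The reporting rule is in Protocol 8.3: "A clinically significant change in laboratory values or vital signs need not be reported as an AE unless the abnormal change constitutes an SAE". The remaining triggers are that the change "leads to discontinuation of treatment or withdrawal from the study". The exemption therefore covers changes that someone has already judged clinically significant.

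The definition is in Protocol 8.1.1: "An AE is the development of an undesirable medical condition (including abnormal laboratory findings) or the deterioration of a pre-existing medical condition". The same section makes the Investigator responsible for recording "all AEs observed by the Investigator or reported by the subject that occur from the day of the biopsy procedure through 24 months", counted from the last injection. SAP 7.2 repeats both statements and does not carry over the 8.3 exemption. SAP 10, which lists differences from the protocol, does not mention the point.

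The primary endpoint in SAP 2.2.1 is "Procedure and/or product related AEs through 24 months post last injection". Relatedness belongs to the AE record. Section 8.3 begins its list of items with "For each AE, the Investigator will record the start date" and goes on to intensity and the Investigator's judgement of relationship. SAP 7.2.3 likewise has relationship to biopsy, injection procedure and product determined for each AE.

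**The concern.** Two sections of the same protocol give a site different instructions for the same finding. Under 8.1.1 an abnormal laboratory finding is an AE and must be recorded. Under 8.3 recording is optional unless the change is serious or ends treatment or participation.

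This matters because the primary endpoint is built only from AEs that carry a relatedness judgement. Protocol 1.7 lists clinically significant anemia, acute kidney injury and acute hypertension among the possible consequences of biopsy and injection. These show up as hemoglobin, creatinine and blood-pressure changes. Protocol 8.2.1 also notes that a severe event need not be serious, so even a severe change can fall under the exemption. The same related change could count toward the primary endpoint for one subject and not for another, depending on which section the site followed.

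**Working it through.** The plan gives no figure on this point, so there is none to reproduce. The check compares the texts, follows one event through the outputs, and sets a scale.

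**1. The texts side by side.**

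| Source | Laboratory change | Vital-sign change |
|---|---|---|
| Protocol 8.1.1, SAP 7.2 | Named as an AE; all AEs recorded | Not named; an AE if it is an undesirable condition or a worsening of an existing one |
| Protocol 8.3 exemption | Optional unless serious, or it ends treatment or participation | Same |
| Protocol 8.3, first paragraph | AEs documented through laboratory reports are recorded | Not named |

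The laboratory conflict is explicit. The vital-sign conflict is inferred.

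**2. One event traced.** Take a hemoglobin fall after an injection that the Investigator would judge clinically significant and related. It is not serious, does not end treatment or participation, and no bleeding diagnosis is recorded.
- Under 8.1.1 it is an AE. It receives a relatedness judgement and enters the related-AE rows of SAP 7.2.5.
- Under 8.3 the site may leave it out. There is then no relatedness judgement, and it appears in no related-AE row.
- SAP 7.2.3 treats a missing relationship as related, but that default acts only on an AE that was entered.

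**3. Where the value still appears.**
- Renal-specific laboratory values, including hemoglobin and creatinine, are secondary endpoints and are summarised by time point (SAP 2.2.2, 6.2).
- SAP 7.3 adds graded abnormality counts up to six months after injection and shift tables to the worst post-baseline value.
- Unscheduled laboratory results are kept out of the table summaries and only listed. Where a visit has retests, only the last value is tabulated or listed, so a transient abnormality followed by a retest can be absent from both (SAP 7.3).
- Baseline is the last value before the first injection (SAP 4.7). A change between biopsy and that injection therefore falls outside the change, graded and shift tables.
- Vital signs have by-visit descriptive statistics, so an extreme at a scheduled visit shows as a minimum or maximum (SAP 4, 7.4). In-procedure and unscheduled readings are only listed.

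None of these outputs carries relatedness, so none can restore the event to the primary endpoint.

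**4. Scale.** SAP 7.2.5 defines incidence as subjects with the event divided by subjects in the analysis set. Leaving out one subject who has no other related AE changes it by x/n − (x − 1)/n = 1/n:
- n = 10 (planned maximum): 10.0 percentage points
- n = 8 (assumed): 12.5 points
- n = 6 (assumed): 16.7 points

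If the subject has another related AE, the overall related-AE incidence does not change and only the episode count falls.

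For context, exact 95% intervals (not planned in the SAP) are 2.5% to 55.6% for 2/10, 0.3% to 44.5% for 1/10 and 0 to 30.8% for 0/10. One omission is small against this imprecision, but it moves the estimate in one direction only.

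**5. Chance that such a change is seen at all.** Let p be the true proportion of subjects with such a change and r the share left unreported. Both are assumptions. With 10 subjects, P(at least one recorded) = 1 − (1 − p(1 − r))^10.

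| p | r = 0 | r = 0.5 |
|---|---|---|
| 10% | 65.1% | 40.1% |
| 20% | 89.3% | 65.1% |
| 30% | 97.2% | 80.3% |

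**The case against.** The best defence is that 8.3 is permissive and the gap is narrow. A site may still report the change. An underlying diagnosis remains an AE, and the first paragraph of 8.3 says that AEs documented through laboratory reports are recorded. Hemorrhage and post-procedure pain are named as events of special interest in 8.1.1.3. Renal laboratory values have their own endpoint tier. The rule also limits noise in subjects who enter with an eGFR of 14 to 20. No hypothesis is tested. CRF instructions are in the Study Reference Manual (Protocol 11.1.1), which is not available here and might settle the matter for sites. All of this stands, and it limits the size of the concern. None of it supplies a relatedness judgement for a change that was never entered.

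Several stronger readings are tempting but not supported:
- A reader might take Protocol 9.7.2, "Clinical and laboratory AEs will be coded using the Medical Dictionary for Regulatory Activities", as a second contradiction. It is compatible with 8.3, because laboratory changes that meet a trigger are still AEs and need coding.
- A reader might cite Protocol 7.2.5, "any worsening from baseline should be reported as an AE if not already documented in medical history". That concerns retinal findings, which are neither laboratory values nor vital signs, so 8.3 does not exempt them.
- A reader might treat the number of procedures whose in-procedure vital signs are only listed as the size of the gap. That reflects SAP 7.4 tabulation, not the effect of 8.3.
- A reader might infer that the laboratory data are lost. They are mostly retained; what is missing is relatedness.

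**Conclusion.** The concern holds as a minor one. For laboratory findings, 8.3 contradicts 8.1.1 and SAP 7.2. For vital signs the conflict is by implication. Followed as written, 8.3 allows a related, clinically significant, non-serious change to be absent from the primary endpoint.

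The effect is 1/n per omitted subject, or 10 percentage points at n = 10. It requires that the site uses the exemption, that the change would have been judged related, that no diagnosis covering it was recorded, and that the subject has no other related AE. The documents give no count of such subjects, so they do not support a claim that the primary result will be understated, only that it can be.

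**What to change.** Replace the 8.3 sentence with a rule of this kind: a laboratory or vital-sign change that the Investigator judges clinically significant is recorded as an AE, with grade and relatedness, whether or not it is serious. The exceptions are a change that is a sign of an AE already recorded, and expected CKD progression or a sedation effect that the Investigator judges not related to biopsy, injection or product. The sentence should state that these are exceptions to 8.1.1, which otherwise counts worsening of a pre-existing condition.

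Issue it by clarification letter, as was done on 25 May 2021 for the eGFR equation (SAP 10), or by amendment if Protocol 10.5 requires one.

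For subjects already treated, Investigators check source laboratory reports and vital signs against the new rule before lock. The SAP laboratory listing is not enough, because it shows only the last retest. Grade and relatedness must be completed for every added AE, since SAP 7.2.2 counts missing intensity as Grade 5 and SAP 7.2.3 counts missing relationship as related. Added AEs are flagged as late-entered in the listing. They fall into the tables already planned in SAP 7.2.5. If the database is already locked, the minimum is to state the limitation beside the primary result.

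The cost is one document and one data check for at most 10 treated subjects. It will bring more AEs, possibly more than a few, because these subjects have advanced disease, are in the study for about 31 months, and under 8.2.1 generate a separate event when a grade changes over time. Some entries will be late in an open-label study. Differences between sites will shrink but not disappear, because the rule still rests on Investigator judgement.
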